c. Cerebrovascular function after SCI. We have recently shown that cardiovascular autonomic dysfunctions after SCI are primary factors that lead to declining health of the cerebral vasculature [19, 20]. Impaired cerebrovascular function and structure are associated with increased risk of stroke as well as cognitive dysfunction [29, 30]. As stroke risk is 200-300% times higher, and cognitive dysfunction occurs in up to 60% of those with SCI [3, 31], a critical appraisal of the association between autonomic dysfunction and cerebrovascular health is needed to improve our understanding and elucidate potential preventative and therapeutic targets. In two seminal clinical trials, we have shown that improving orthostatic hypotension using midodrine improves cerebrovascular function, orthostatic tolerance, and cognition [32, 33]. These studies provide strong evidence that mitigating orthostatic hypotension can improve cerebrovascular function and associated clinical conditions. Therefore, there is a dire need for a novel intervention aimed at reducing cardiovascular dysfunction in those with SCI, as this has the potential to reduce cardiovascular disease risk, improve cerebrovascular function and restore cognition in this population. scES, when optimized for improving cardiovascular function is hypothesized to increase blood pressure and reduce the severity of orthostatic hypotension, which will provide a similar benefit to presser pharmacological agents after SCI, and partially restore normal cerebrovascular function and cognition in those living with SCI.

3. Bladder, Bowel and Sexual Function. Bladder, bowel and sexual dysfunctions rank among the top disorders affecting quality of life after SCI [34, 35]. We have exciting new preliminary data from several individuals with severe injuries to support recent intriguing case reports indicating improved bladder and bowel function as well as improved sexual function after undergoing an activity-based rehabilitation, locomotor training, and scES in combination with locomotor training. In addition, we have observed dramatic interference with stepping ability when the individual's bladder is full, suggesting interaction of locomotor and bladder circuitry.

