The EQ-5D-3L captures an individual's self-reported health status at the time they complete the questionnaire. The EQ-5D-3L consists of 2 pages – the EQ-5D descriptive system and the EQ visual analogue scale (EQ-VAS). The EQ-5D-3L descriptive system comprises the following 5 dimensions: mobility, self-care, usual activities, pain/discomfort and anxiety/depression. Each dimension has 3 levels: no problems, some problems, extreme problems. The respondent is asked to indicate his/her health by ticking (or placing a cross) in the box against the most appropriate statement in each of the 5 dimensions. The EQ VAS records the respondent's self-related health on a vertical, visual analogue scale where the endpoints are labeled 'Best imaginable health state' and 'Worst imaginable health state.' This information can be used as a quantitative measure of health outcome as judged by the individual respondents [96]. Furthermore, we will conduct qualitative interviews.

Methods: In this study, we will employ SCI-FI scales to examine intervention impacts on the following quality of life domains: Basic mobility, Self-care, Fine Motor Function, Wheel Chair Mobility, and Ambulation. The SCI-QOL measures include: Bladder Management, Bowel Management, Pain Interference, Depression, Anxiety, Resilience and Ability to Participate in Social Roles/Activities. We will also administer the PROMIS global satisfaction with sexual function along with the Pure Pain Scale and the Revised Life Events Survey. We may assess these pre-usual care, post-interventions and during follow-ups.

Additionally, we will employ the EQ-5D-3L scales to examine the intervention impacts on the following quality of life domains: mobility, self-care, usual activities (e.g. work, study, housework, family or leisure activities), pain/discomfort, and anxiety/depression. Finally, we will conduct qualitative interviews using an interview guide developed specifically for this study that has been pilot tested.

Specific Aim 5.

Measure impact of scES and training on healthcare resource utilization.

Secondary Analyses:

Hypothesis 5a: Healthcare resource utilization will decrease with scES.

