Rationale: SCI injuries are often accompanied by respiratory, cardiovascular, bladder, bowel and sexual dysfunction requiring greater healthcare utilization. The economic impact on the increased use of healthcare can be devastating. It is estimated that the total cost of care in the years after the first year of injury is \$165,554. The total cost of care includes the cost of hospitalization each year, nursing home care, outpatient services, physician fees, equipment, environmental modifications, supplies, attendant care, and vocational services [97].

Methods: We will collect healthcare resource utilization information from each research participant's insurance provider from two years prior to the intervention to two years after the intervention. We will also enroll a control group to more precisely estimate changes in resource utilization. The control group will be selected from the Neurorecovery Network (NRN) and will be enrolled under a separate protocol. Patients with complete or incomplete cervical or thoracic SCI are referred to the NRN and there receive intense locomotor training for three to four months. Controls will be matched on age, level of severity, duration of injury, and insurance type. Resource utilization data will be assigned to one of the cost categories above and a cost estimate will be assigned to the resources.

D. Outcomes

1. Functional Movement Assessments (Voluntary movement of legs and trunk)

a. Multi-Segmental Motor Responses (MMR)

Procedure: Motor responses in different leg muscles can be evoked by non-invasive stimulation of the dorsal lumbosacral spinal cord and recorded [98-100]. Such Multisegmental Monosynaptic Reflexes (MMR) [101, 102] are the basic components of the lower-limb muscle responses that are elicited by epidural stimulation of posterior lumbar cord structures. MMRs will be evoked by stimulating the spinal cord percutaneously between the T9 and L4 spinous processes. The AgCl cathode (pre-gelled, soft surface electrode) will be placed over the skin between T9 and T10, T10 and T11, T11 and T12, T12 and L1, L1 and L2, L2 and L3, and L3 and L4 spinous processes and two 50 x 100 mm large anodes will be placed bilaterally over the anterior spine of the iliac crest. The optimum site of stimulation will first be located by a hand-held electrode. The site of stimulation will be selected based on where the motor responses can be elicited in all the recorded muscles as

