In addition to securing scientific advances, our proposed experiments are essential to translating this novel therapeutic approach to a larger scale, and to expand its clinical impact. Therapy using scES for recovery of neurological function in patients with severe SCI is not widely used because of uncertainty regarding the mechanisms of action and convincing evidence of efficacy in larger numbers of subjects. Our approach will allow us to determine the specific types of scES needed for recovery of voluntary movement and autonomic nervous system dysfunction, and this will lay the groundwork for expedient translations to treatment of other neurologic disorders and disease that cause paralysis, including stroke, traumatic brain injury, movement disorders and cerebral palsy.

IV. Human Subjects

A. Human Subjects Involvement and Characteristics.

There are approximately 1,275,000 Americans with a SCI. Fifty-six percent of the injuries occur in people aged 16 to 30, with an average age of 31, and 82% of the total population are male. Minorities make up 38% of SCI cases, and while every effort will be made to recruit minorities, based on the incidence rates, their participation may be limited. Every effort will be made to recruit women, though only about 18% of SCI patients

are female. Pregnant women with SCI will not be studied because the risks to the fetus are unknown. No other vulnerable subjects will be included.

We will recruit and screen approximately 108 individuals to reach an enrollment in the proposed study of 36 research participants who have sustained a severe SCI. We anticipate we will need to pre-screen approximately 200 individuals to identify 108 for screening. Frazier Rehab Institute evaluates approximately 300 chronic SCI outpatients each year. We also have a database of over 5,000 people with SCI who have expressed interest in participating in our research programs. We will select individuals to assure that there are a minimum of 25% (n=9) women to adequately represent the percentage in the SCI population.

Inclusion/Exclusion Criteria.

All research participants, irrespective of gender, will be selected based on the following criteria:

Inclusion criteria:

- 1) At least 18 years of age
- 2) non-progressive SCI
- 3) at least 2 years post injury
- 4) stable medical condition
- 5) unable to voluntarily move all individual joints of the legs
- 6) unable to stand independently

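### Aim 5 compares scES with locomotor-trained controls, so it does not isolate scES against usual care, and its two-year pre-window can reach into the first year after injury

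*Protocol*

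**What the plan says.** Protocol section III.C, Specific Aim 5, states the claim as "Hypothesis 5a: Healthcare resource utilization will decrease with scES". It is listed as a secondary analysis, and the aim itself is worded as the impact of scES and training together.

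The Methods paragraph takes utilisation data from each participant's insurer "from two years prior to the intervention to two years after the intervention". It continues: "We will also enroll a control group to more precisely estimate changes in resource utilization". On the source of these controls it says "The control group will be selected from the Neurorecovery Network (NRN) and will be enrolled under a separate protocol", and that people with complete or incomplete cervical or thoracic injury "are referred to the NRN and there receive intense locomotor training for three to four months". On comparability: "Controls will be matched on age, level of severity, duration of injury, and insurance type".

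The inclusion criteria in section IV.A require only "at least 2 years post injury", with no upper limit. The Aim 5 rationale quotes an annual cost of care for the years that follow the first ($165,554) and gives no figure for the first year.

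**The concern.** Two features fixed in this protocol affect what Aim 5 can conclude.

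**Comparator.** Hypothesis 5a speaks of scES, but the control group is actively treated. The Aim 5 rationale attributes utilisation to respiratory, cardiovascular, bladder, bowel and sexual dysfunction. Section II.B.3 reports "improved bladder and bowel function as well as improved sexual function after undergoing an activity-based rehabilitation, locomotor training", so on the protocol's own account the control treatment may act on the same functions. That support is modest: it rests on case reports and preliminary data from several individuals, and the same sentence goes on to include scES combined with locomotor training. The controls' change still cannot be read as the change expected under usual care.

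**Pre-window.** A two-year look-back combined with entry from two years after injury lets first-year utilisation into the baseline of recently injured participants. If utilisation is higher in the first year, the before-after change is a fall whether or not scES does anything. Hypothesis 5a, worded as a decrease, would then look confirmed.

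**Working it through.** Aim 5 states no sample size, power or effect figure, so there is nothing of the plan's own to reproduce. The check is calendar arithmetic plus one assumed ratio.

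**Inputs**
- Minimum time since injury: 2 years = 730 days (section IV.A, criterion 3).
- Criteria 1 to 4 are judged at screening (section III.B.1.c). All criteria are checked again after Usual Care (section III.B.2).
- Usual Care: at least 80 days (section III.B.2).
- Recovery at home after surgery: 2 to 3 weeks = 14 to 21 days (section III.B.3.a).
- Pre-window: 730 days before the intervention, taken here as the start of intervention 1.
- r = utilisation rate in the overlapping part of the first year divided by the later rate. **Assumed**, range 1.5 to 3.

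**Step 1: overlap with the first year**

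Window start = (days since injury at intervention start) − 730. Overlap O = max(0, 365 − window start).

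| Case | Intervention starts, day | Window starts, day | O, days | O/730 |
|---|---|---|---|---|
| 2 years met at screening, 14-day recovery | 730+80+14 = 824 | 94 | 271 | 37% |
| Same, 21-day recovery | 831 | 101 | 264 | 36% |
| 2.5 years (913 days) at screening | 913+94 = 1007 | 277 | 88 | 12% |
| 3 years at intervention start | 1095 | 365 | 0 | 0% |

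Any further delay before the intervention shortens the overlap, so 271 days is the most that screening-based eligibility allows.

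**Step 2: before-after fall with no treatment effect**

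Set the later rate to 1. The pre-period mean is (O·r + 730 − O)/730, the post-period mean is 1, and the fall is 1 − 1/(pre-period mean).

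For O = 271:
- r = 1.5: pre = (406.5 + 459)/730 = 1.186, fall 16%
- r = 2: pre = (542 + 459)/730 = 1.371, fall 27%
- r = 3: pre = (813 + 459)/730 = 1.742, fall 43%

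For O = 88 the falls are 6%, 11% and 19%. For O = 0 they are zero.

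**Step 3: what duration matching does**

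The spurious between-group difference in change, in later-year units, is (O of control − O of participant)·(r − 1)/730.
- Control indexed at the same time since injury: 0.
- Control indexed 90 days later (O = 181 against 271): −90/730 = −0.12 for r = 2 and −180/730 = −0.25 for r = 3. This favours scES and is a third (90/271) of the uncontrolled artefact. A control indexed earlier reverses the sign.

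**Step 4: direction of the comparator effect**
- If locomotor training lowers controls' utilisation, the contrast understates scES.
- If the training itself counts as utilisation in the controls' post-period, the contrast favours scES.
- If it counts in their pre-period, controls show an artificial fall and the contrast works against scES.

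The Aim 5 text gives neither the controls' index date nor a rule for counting the training, so the net direction cannot be read from it.

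**The case against.** The strongest defence has four parts.

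**A trained comparator is a legitimate choice.** Participants train intensively too, and Aim 5 is worded as scES and training. If locomotor training lowers utilisation, the comparison is conservative, and a larger fall than in controls would still support scES. This stands. A reader might infer that a fall with scES cannot be attributed at all, and the documents do not support that. They support the narrower statement that the contrast is against locomotor training, not usual care.

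**The overlap is a boundary case.** It touches only people under three years post injury at intervention start. Recruitment follows the order of entry into the database, with previously screened people contacted first (section III.B.1.a), which may make entry at the minimum uncommon. This also stands: the percentages describe one participant, not the trial.

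**Duration is matched.** It is, and exact matching cancels the artefact between groups. But 5a is worded as a decrease, and controls are introduced to sharpen the estimate, not as the stated basis of the test.

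**Index dates and claim rules may lie in the separate control protocol or the SAP.** Neither is at hand, so their absence here is not counted as a fault. The control source, data window, entry limit and hypothesis are fixed in this document.

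Two further inferences are tempting and unsupported. One is a billing asymmetry: the arrangement that keeps tests out of insurance billing (section III.B.1.b) covers only pre-screening tests, and nothing says NRN training is billed to insurers. The other is that the research database offers untrained controls: section III.B.1.a says some of its members have completed earlier studies.

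**Conclusion.** The point holds in limited form. The between-group contrast in Aim 5 estimates scES plus its training against three to four months of locomotor training, so it does not isolate scES against usual care.

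The two-year pre-window can also include up to about 271 of 730 days of first-year utilisation. For a participant at that limit, this produces a 16% to 43% before-after fall with no treatment effect. That range rests on the assumed ratio of 1.5 to 3 and on eligibility first being met at screening. A fall near 49% would require the two-year criterion to be first met at randomisation (O = 351 days) together with r = 3. Since the protocol judges that criterion at screening, this is the less natural reading.

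The trial-level effect could be anything from nil upwards, because the distribution of time since injury is not stated. It is nil if everyone is at least three years post injury at intervention start. In a between-group contrast it also vanishes if controls are indexed at the same time since injury.

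**What to change.** In section III.C, Specific Aim 5:
1. Start the pre-window at the later of two years before the intervention and 12 months after injury, in both groups, and analyse annualised rates over the person-time that remains.
2. Index each control at the matched participant's time since injury.
3. Test Hypothesis 5a as the between-group difference in change, with NRN training claims excluded at least in a sensitivity analysis.
4. State the conclusion as scES plus training versus locomotor training.

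The cost is wording and claims programming, with no change to enrolment or treatment. A participant at the earliest entry keeps 730 − 271 = 459 pre-period days (63%), so baseline rates for recently injured people are less precise. The claim also becomes narrower than Hypothesis 5a as now worded.

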Procedures: Assess specific leg and trunk muscle electromyography (EMG) and force generation during targeted intentional movements. EMG, kinematic and kinetic analysis may be performed on the lower extremities and/or trunk during voluntary movement attempts with and without Voluntary-scES. Lower extremity and trunk muscle activation patterns will be evaluated using EMG soleus (SOL), medial gastrocnemius (MG), tibialis anterior (TA), medial hamstrings (MH), quadriceps (VL and RF), adductor (AD) and/or of related muscles using the MA300 System (Motion Lab Systems, Baton Rouge, LA) .EMG input will be amplified with a gain of 2000, filtered at 4-1000 Hz and sampled at 2000-10000 Hz. The bipolar surface electrodes will be placed over the muscle belly parallel to the muscle fibers. The skin will first be prepared by shaving and cleaning the area with a sterile alcohol swab before electrode placement. The ground electrode(s) will be placed over a bony surface of the lower leg bilaterally. We may also use fine-wire EMG to acquire activity from the illio-psoas, extensor hallicus longus, extensor digitorum longus or other deep muscles muscle. Standard needle insertion sites for each muscle will be used [106]. Limb kinematics may include hip, knee and ankle angles that will be acquired using high speed passive marker motion capture (Motion Analysis, Santa Rosa, CA). Force generation will be measured with force transducer via a non-elastic cable throughout all supine movements (flexion and extension of the toes, ankles, knees and hips). Blood pressure and heart rate may be measured using either a manual blood pressure monitor (Dinamap V100, GE Medical) or by a finger cuff (Finapres Medical Systems). Temperature may be monitored using a customized sensor system.

Participants will be in a supine or sitting position. Participants will be asked to perform voluntary movements in response to verbal commands, visual cues or auditory cues. We will ask participants to perform movements requiring different levels of precision and endurance. Blood pressure and heart rate may be measured using either a manual blood pressure monitor (Dinamap V100, GE Medical) or by a finger cuff (Finapres Medical Systems). This may be done with scES.

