Analysis: Efficacy in voluntary movement will be measured by calculating peak force relative to stimulation amplitude. Task specific leg muscle electromyography outcomes (amplitude, duration, and onset and offset) appropriate for the movements will also be used to assess quality of movement. EMG data will be full wave rectified and filtered using a 4th order bandpass Butterworth filter (40 Hz - 500 Hz) representing the relative number and frequencies of the motor units recruited per burst. Integrated EMG will assess the total EMG activity generated during specific phases of the motor tasks. Co-activation values of agonists and antagonist muscles and the degree of coordination in the movements will be evaluated through principal component analysis. Other comparisons used in the analysis will include amplitude and duration of force generation; rate of movement; and accuracy of movement. Accuracy of movement relative to visual and auditory cues will be analyzed by slope and shape comparison between the computer generated signal and those produced by the movement [107].

e. Lower Extremity Torque Assessment with Electromyography (EMG)

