Analyses: Torque characteristics including mean, peak, and integrated torque, torque duration, and torque derivation of voluntary and electrical stimulation attempts will be calculated using customized Labview (National Instruments, Austin, TX) software. Efficacy in voluntary movement will be measured by calculating peak force relative to stimulation amplitude. Task specific leg muscle electromyography outcomes (amplitude, duration, and onset and offset) appropriate for the movements will also be used to assess quality of movement. Electromyography data will be full wave rectified and filtered using a 4th order bandpass Butterworth filter (40Hz - 500 Hz) representing the relative number and frequencies of the motor units recruited per burst. Integrated electromyography will assess the total electromyography activity generated during specific phases of the motor tasks.

2. Cardiovascular.

a. Ambulatory BP and Heart Rate monitoring.

Procedure: Twenty-four hour ECG will be performed using Edan 3-channel Holter with continuous heart rate monitoring. Twenty-four-hour ABPM will be performed using the ABPM-05 (Meditech) monitor. The device will be fixed with appropriate cuff sizes to the non-dominant arm and pre-programmed such that systolic blood pressure (SBP), diastolic blood pressure (DBP), and heart rate (HR) will be recorded automatically every 15 minutes during their daytime active period, then hourly overnight. For participants who have a scheduled bowel routine within the 24-hour monitoring period, recordings at 5-minute intervals for 30 minutes before, during, and for 30 minutes after the routine will be programmed. Additionally, participants will be instructed to initiate a self-measurement any time they experience symptoms of or completed an activity that may trigger a hypo- or

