signaled the subject to begin the task. The overall amount of EMG Magnitude (μ V, Mag) and the Similarity Index (SI), that quantitate the multi-muscle distribution of activation during Maximum Expiratory Pressure Task (MEPT) in research participants compared to that of healthy subjects will be calculated using a vector-based analysis as previously described [126, 127]. In brief: multi-muscle activity parameters will be calculated using averaged RMS amplitudes from each SCI subject for comparison to group values from non-injured (NI) subjects. The resulting Mag parameter is the amount of combined sEMG activity during MEPT calculated as a length of the resultant vector. The SI provides a value between 0.0 and 1.0 (most similar) equal to the cosine of the angle between the resultant multi-muscle distribution vectors in SCI subject to that of NI subjects. To perform the maximum airway pressure tasks, subjects will produce maximum respiratory efforts for 5 seconds blowing into the Airlife 001504 circuit (Allegiance Healthcare Corp., McGaw Park, IL). Airway pressure; sEMG; breathing rate and chest wall kinematics will be monitored simultaneously by using Powerlab acquisition system (ADIInstruments, Colorado Springs, CO).

For the bursts analysis, EMG data will be full wave rectified and filtered using a 4th order bandpass Butterworth filter (40 Hz - 500 Hz) representing the relative number and frequencies of the motor units recruited per burst. Integrated EMG will assess the total EMG activity generated during specific phases of the motor tasks. Co-activation values of inspiratory and expiratory muscles and the degree of coordination in the breathing-related oscillations will be evaluated through principal component analysis.

c. Resting Metabolic Rate (RMR).

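### Four EMG analysis sections name rectification before a 40-500 Hz band-pass; followed in that order, integrated EMG and co-activation lose the burst envelope (low severity, one-sentence fix)

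*Protocol*

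**What the plan says.** The voluntary movement section (Protocol III.D.1.d) and the standing section (III.D.3.a) state: "EMG data will be full wave rectified and filtered using a 4th order bandpass Butterworth filter (40 Hz - 500 Hz". The torque section (III.D.1.e) has "Electromyography data will be full wave rectified and filtered using a 4th order bandpass Butterworth filter (40Hz - 500 Hz", and the respiratory motor control section (III.D.4.b) has "For the bursts analysis, EMG data will be full wave rectified and filtered using a 4th order bandpass Butterworth filter (40 Hz - 500 Hz". The filtered signal is described as "representing the relative number and frequencies of the motor units recruited per burst".

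The next step in III.D.1.d, III.D.3.a and III.D.4.b is "Integrated EMG will assess the total EMG activity generated during specific phases of the motor tasks"; III.D.1.e says the same with the abbreviation spelled out. III.D.1.d, III.D.3.a and III.D.4.b also derive muscle co-activation and coordination by principal component analysis. None of the four sections says which signal is integrated, mentions a second rectification, or gives the steps in the other order.

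At acquisition the EMG is "filtered at 4-1000 Hz and sampled at 2000-10000 Hz", so the 40-500 Hz filter is a later processing step. In III.D.1.d and III.D.1.e the efficacy measure is something else: "Efficacy in voluntary movement will be measured by calculating peak force relative to stimulation amplitude". EMG there serves as a further measure of movement quality.

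**The concern.** Raw EMG swings around zero, and its size lies in how wide the swings are. Full-wave rectification turns that width into a positive mean and a slowly varying envelope. For bursts lasting seconds, both lie far below 40 Hz. A linear band-pass with a 40 Hz lower edge has zero gain at zero frequency, so if it is applied after rectification it returns a signal centred on zero. The area under that signal no longer measures total activity. Two muscles that switch on and off together also lose the shared slow pattern that a principal component analysis of co-activation would pick up.

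At stake is the meaning of the integrated EMG and co-activation results in these assessments. So is comparability: an analyst following the written order and one using the conventional order would report different values from the same recordings.

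**Working it through.** The protocol gives no figure to reproduce, so the check is a signal simulation.

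**Inputs from the protocol.** 4th-order Butterworth band-pass, 40-500 Hz; sampling at 2000 and 10000 Hz (the two ends of the stated range).

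**Assumptions not in the protocol.** EMG is Gaussian noise band-limited to 20-450 Hz, with one 2 s burst on a near-silent baseline. Burst SD is 10, 50, 100 or 200 arbitrary units, the filter is zero-phase, and there are 40 runs per setting.

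**Quantities, each integrated over the burst.** With x the raw signal and BP the band-pass:
- R = ∫|x| (rectified only)
- S = ∫BP(|x|) (written order, plain integral)
- T = ∫|BP(|x|)| (written order, rectified a second time)
- C = ∫|BP(x)| (band-pass, then rectify)

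**Results at 2000 Hz (means).**

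| Burst SD | R | S | T | C | S/R | T/R | C/R | T/C |
|---|---|---|---|---|---|---|---|---|
| 10 | 15.881 | 0.018 | 7.669 | 15.145 | 0.11% | 48% | 95% | 51% |
| 50 | 79.708 | 0.089 | 38.388 | 75.932 | 0.11% | 48% | 95% | 51% |
| 100 | 159.506 | 0.171 | 76.853 | 151.911 | 0.11% | 48% | 95% | 51% |
| 200 | 318.402 | 0.351 | 152.892 | 303.306 | 0.11% | 48% | 95% | 50% |

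**Noise (SD over runs divided by mean).** At burst SD 10, S gives 0.006/0.018 = 33% and C gives 0.233/15.145 = 1.5%. At burst SD 200, S gives 0.133/0.351 = 38% and C gives 4.952/303.306 = 1.6%.

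**Sensitivity.**
- At 10000 Hz and burst SD 10: S/R = 0.017/15.714 = 0.11%, T/R = 7.445/15.714 = 47%, C/R = 14.675/15.714 = 93%.
- With a causal filter, the mean absolute value of S is 0.03-0.04% of R. Its mean lies around zero and is smaller than its spread (at 2000 Hz, burst SD 200: mean -0.027, SD 0.165).
- Under three other assumed spectra with the zero-phase filter, S/R was 0.11-0.13%. T/C was about 50% for a 20-450 Hz spectrum, 51% for 50-300 Hz, and 56-57% for narrower low-frequency spectra. The shortfall after a second rectification therefore depends on spectral content and is not a fixed factor.

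**Co-activation.** Two simulated muscles with independent noise and a common envelope had a correlation of 0.36, which fell to 0.00 in the written order. The starting value depends on the assumed envelope. A re-run with other envelopes also ended at about zero. No choice of integration is involved.

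**The case against.** **The order is inferred.** The steps are joined by a plain conjunction, so the sentence may be a list. The four occurrences are near-identical wording, so they are not four independent confirmations. The team may in practice band-pass the raw signal first. This stands as a caution about intent. It does not remove the point: rectification is named first every time, the other order never appears, and the rule gives a wrong result if followed as written.

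**Near-zero integrals also need a plain, signed integral.** This is correct. A reader might infer that burst amplitude is destroyed, or that the result is the same whatever the effort. Neither is supported. T rises from 7.669 to 152.892, or 19.9-fold, for a 20-fold rise in burst SD. With the zero-phase filter even the small residual S grows with amplitude. But T needs a second rectification that the four sections do not mention. Where the protocol wants a rectified area or an RMS envelope it says so, in III.D.1.a and in the first part of the III.D.4.b analysis. The co-activation loss does not depend on this choice.

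**The trial's hypotheses are not shown to be harmed.** This also stands. A reader might infer that the voluntary movement, standing and respiratory hypotheses lose their treatment signal, but the hypotheses do not name integrated EMG. Efficacy in III.D.1.d and III.D.1.e is peak force relative to stimulation amplitude. Appendix 1 schedules those two assessments only from after implantation, so their EMG could not supply a Usual Care comparison in any case. The Functional Neurophysiological Assessment (III.D.1.b) names no 40-500 Hz step. Standing independence has its own line in Appendix 1. Spirometry and airway pressures use no EMG, and the respiratory Magnitude and Similarity Index use RMS amplitudes.

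**This is detail for a script or the SAP.** Silence on the order could have been left there. Here the protocol itself states the steps, so its wording should be right.

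**Conclusion.** The point holds at low severity. Taken in the written order, with the plain integral that the text implies, integrated EMG keeps about 0.1% of the rectified integral and has a coefficient of variation of about one third. The conventional order keeps about 95%, with a coefficient of variation of about 1.5%. Shared-envelope co-activation is lost in III.D.1.d, III.D.3.a and III.D.4.b. If the filtered output were rectified again, the measure would follow effort but at about half the standard value.

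The percentages rest on assumed Gaussian EMG and assumed spectra, and the causal-filter figure is smaller still. That the mean and slow envelope are removed follows from the filter itself and does not depend on those assumptions. The effect is confined to supporting measures: EMG quality of movement, standing EMG and the respiratory burst analysis. Nothing is permanently lost, because raw recordings can be reprocessed. The protocol does not show which order the scripts actually use.

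**What to change.** In III.D.1.d, III.D.1.e, III.D.3.a and III.D.4.b (burst analysis), replace the processing sentence with: *Raw EMG will be band-pass filtered (4th-order Butterworth, 40-500 Hz), then full-wave rectified; integrated EMG is the integral of the rectified signal over the task phase.* State that the same steps apply at all visits and that the co-activation analysis starts from the same rectified signal. Check the analysis scripts against this text, and reprocess stored raw recordings if any were handled in the other order.

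The cost is one sentence in four places and a script check. No new data, visits or participants are needed.
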